Statistical Analysis Plan

NCT01682356

December 7, 2023

Statistical Analysis Plan

Isometric testing: This will be conducted at a knee angle of 1.22 rad (70°). After the final rest period, subjects will perform an all-out 50 contraction fatigue test (at 3.14 rad/s) to determine whether dietary NO₃ – influenced fatigue during repetitive, maximal muscle activation. Torque data will be windowed and smoothed using the manufacturer's software, after which the highest torque will be generated at each velocity which will be used to calculate peak power at that velocity. The peak power–velocity data will be fit with a parabolic function to determine maximal knee extensor power and velocity. All statistical analyses will be performed using GraphPad Prism version 6.05 (GraphPad Software, La Jolla, CA). Normality of data distribution will be first tested using the D'Agostino–Pearson omnibus test. Data will be subsequently analyzed using 2-way (treatment x order) ANOVA, with the subject as a repeated measures factor within treatment. A P value of <0.05 will be considered significant. Sample size will be chosen based on our recent study of the effects of dietary NO₃ – on muscle power in healthy individuals and will enable us to detect any effect size of ≥ 0.69 with a power (ie, $1-\beta$) of 0.80 at an α of 0.05 assuming a within-subject correlation of 0.95. Primary outcome variables will be changes in breath NO and peak and maximal muscle power and velocity in response to dietary NO₃; all other variables measured will be considered secondary.

VO₂ testing:

Respiratory gas exchange data will be collected during the final 2 minutes of each stage of the submaximal exercise test will be averaged and used in all subsequent analyses. Gross efficiency will be calculated as the ratio of external power to metabolic power, multiplied by 100%. Delta efficiency (ie, the slope of the relationship between external and metabolic power) and the metabolic cost of unloaded cycling (ie, the y intercept of this relationship) will be determined by regression analysis. During the maximal exercise test the oxygen uptake efficiency slope will be calculated by regressing VO₂ (in L/min) on the log of ventilation (Ve; also in L/min), both will be measured at 15-second intervals. The Ve/carbon dioxide production (VCO₂) slope will be calculated in a similar fashion. VT will be determined using the V-slope method. Peak power will be defined as the average power during the last 1 minute of exercise. VO_{2peak} was defined as the highest VO₂ will be measured over any 1-minute period. Statistical analyses will be performed using GraphPad Prism, version 7.02 (GraphPad Software, La Jolla, CA). Normality of data distribution will first be tested using the D'AgostinoPearson omnibus test. Data will be subsequently analyzed using 2-way (treatment \times order) analysis of variance, with subject as a repeated measures factor within treatment. A P value <.05 will be considered significant. Primary outcome variables will be changes in ventilatory responses and VO_{2peak} in response to dietary NO₃. Secondary outcome variables will be changes in exercise performance and efficiency; all other variables measured were considered tertiary.

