- 2) Subjects will be asked to answer questionnaires regarding their medical health (basic health questionnaire, Minnesota Living with Heart Failure questionnaire, a combined fatigue questionnaire, a magnetic resonance safety questionnaire -i.e., questions regarding implanted pacemakers, etc.). Subjects will have a physical examination.
- 3) Subjects will be instructed by study personnel to minimize dietary intake of foods that are high in dietary nitrates the day before each study visit.
- 4) During study visit #1, subjects will be randomized to receive either one to two "shots" of BRJ (James White Drinks) or placebo (BRJ without nitrates).
- 5) Before and at 3 time points after receiving the BRJ or placebo, subjects will undergo phlebotomy for plasma nutrient/hormone levels and genetic testing and will have their blood pressure checked and will blow into a tube connected to a small machine that will measure the amount of nitric oxide in their breath.
- 6) Subjects will undergo transthoracic echocardiographic imaging at rest. They will also have their body composition determined via DXA.
- 7) ~2 h after ingestion, subjects will blow into another machine to measure their respiratory muscle function.
- 8) Subjects will pedal a cycle ergometer for 6 min at ~50, ~60, and ~70% of $\dot{V}O_2$ peak while $\dot{V}O_2$ is measured using a ParvoMedics TrueOne metabolic cart. The average $\dot{V}O_2$ during the last 2 min of each stage will be used to calculate gross and delta efficiency using stoichiometric equations as previously described. Following a 10 min rest period, peak power and $\dot{V}O_2$ peak will be determined during a continuous exercise test performed using a 10 W/min ramp protocol. Subjects will have their blood pressure, heart rate and rhythm monitored during this study. They will also have their muscle oxygen levels measured using small sensors taped to their thighs.

- 11) Subjects will undergo a 7 d washout period.
- 12) Subjects will come in for study day 2 in which they will receive whichever treatment (BRJ or placebo) they did not receive at first and then repeat the studies listed above 5-11).

II. BRJ neuromuscular function testing sub-study:

- 1) Subjects will be asked to undergo steps 1-7 of the main study described above.
- 2) Subjects will undergo a test of neuromuscular function using an isokinetic dynamometer (a device that measures voluntary muscle force production while controlling the speed of movement).

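### Do the SAP's slope and y-intercept definitions of delta efficiency and unloaded cycling cost conflict in a way that calls for a change?

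*SAP*

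**What the plan says.** The SAP, under VO2 testing, derives the efficiency variables from the submaximal cycling stages. It first fixes the simple ratio: "Gross efficiency will be calculated as the ratio of external power to metabolic power, multiplied by 100" percent. It then takes two further quantities from a single fitted line: "Delta efficiency (ie, the slope of the relationship between external and metabolic power) and the metabolic cost of unloaded cycling (ie, the y intercept". The intercept is explicitly that of the same line: "the metabolic cost of unloaded cycling (ie, the y intercept of this relationship) will be determined by regression analysis". It does not say which power is the dependent variable, and it mentions neither a reciprocal nor an x intercept.

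A few lines later the SAP does give the direction of a different regression: "the oxygen uptake efficiency slope will be calculated by regressing VO₂ (in L/min) on the log of ventilation". It ranks the outcomes as follows: "Secondary outcome variables will be changes in exercise performance and efficiency; all other variables measured were considered tertiary".

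Protocol section F2, step 8 of the main study, gives the data behind each line: "Subjects will pedal a cycle ergometer for 6 min at ~50, ~60, and ~70% of" peak oxygen uptake, so three points per subject and visit. For the method it says only that the oxygen uptake data "will be used to calculate gross and delta efficiency using stoichiometric equations as previously described". Protocol sections G3 and G4 refer to the publications for statistical methods.

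**The concern.** A slope and a y intercept belong to one fit with one pair of axes, and here the two labels point to opposite pairs. An analyst who follows the words literally has to mislabel one of the two quantities. The SAP names the direction for the oxygen uptake efficiency slope, so the silence here looks like an oversight.

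Two things could go wrong. If external power is put on y and the y intercept is reported as the unloaded cost, that number mixes unloaded cost with delta efficiency and can move when only delta efficiency changes. If metabolic power is put on y and the raw slope is reported as delta efficiency, a better efficiency appears as a lower value. Change in efficiency is a declared secondary outcome of the VO2 study, so a reversed sign would matter if it reached a report.

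**Working it through.** The documents give no figure to reproduce. The check is algebraic, and every watt value below is an assumption used for illustration.

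**Model.** Let E be external power, M metabolic power, U the unloaded metabolic cost and DE delta efficiency (change in E per change in M). Then M = U + E/DE, or equivalently E = DE × M - U × DE.

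- External power on y: slope = DE; y intercept = -U × DE.
- Metabolic power on y: slope = 1/DE; y intercept = U.

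There is no third arrangement, so the mismatch does not depend on any number.

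**Illustration.** Assume U = 150 W, DE = 0.25 and E = 25, 37.5 and 50 W. Then M = 150 + E/0.25 = 250, 300 and 350 W, which is in the ratio 50:60:70.

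- E on M: slope = (50 - 25)/(350 - 250) = 0.25; y intercept = 37.5 - 0.25 × 300 = -37.5 W.
- M on E: slope = (350 - 250)/(50 - 25) = 4.0; y intercept = 300 - 4.0 × 37.5 = 150 W.

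**Range.** For U from 100 to 200 W and DE from 0.20 to 0.25, the E-on-M intercept runs from -100 × 0.20 = -20 W to -200 × 0.25 = -50 W. The M-on-E slope runs from 1/0.20 = 5.0 to 1/0.25 = 4.0.

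**Effect of a literal reading.** Let DE rise from 0.25 to 0.26 with U fixed at 150 W. The E-on-M intercept moves from -37.5 to -150 × 0.26 = -39.0 W, a 4% shift although the unloaded cost has not changed. The M-on-E slope falls from 4.00 to 1/0.26 = 3.85, so an improvement shows as a decrease.

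**Would this go unnoticed?** Gross efficiency from the same stages is 25/250 = 10%, 37.5/300 = 12.5% and 50/350 = 14.3%. A delta efficiency of 400% beside these values, or a negative metabolic cost, is plainly impossible.

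**What the text implies.** A metabolic cost is an amount of metabolic power, and it can be a y intercept only if metabolic power is on y. The gross efficiency definition fixes efficiency as external over metabolic power. Delta efficiency must therefore be the change in external power over the change in metabolic power, which is 1/slope of that line: 1/4.0 = 0.25. With this reading both quantities come out correctly (25% and 150 W). The reverse fit gives the same pair if the cost is taken as the x intercept: -(-37.5)/0.25 = 150 W.

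**The case for a change.** The strongest case for a change is that the implied reading supplies an inversion the SAP does not state. The two valid conventions also stop being identical once there is measurement error, because the E-on-M slope equals r² times the reciprocal of the M-on-E slope, and with only three stages r² is below 1. In a simulation assuming a true delta efficiency of 25% and 3% random error in metabolic power, the E-on-M slope had median 24.6% and mean 25.0%; 100/slope of M on E had median 25.0% and mean 25.4%. In a second simulation (assumed E of 30, 45 and 60 W, U of 200 W), the medians were 0.2496 against 0.2505 at an error SD of 5 W and 0.2367 against 0.2510 at 20 W. A prespecified plan could close this freedom in one sentence.

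The algebraic part of this stands: the sentence is not literally correct. The practical part does not carry far. Calling the cost a y intercept already points to the M-on-E fit, so the direction is not really open. The simulations do not show that one direction is better for delta efficiency, since the median favours one and the mean the other. If measurement error is similar on the two study days of this crossover, either convention acts alike on both treatments and creates no difference between them. The harmful readings require someone to report negative watts as a metabolic cost, or several hundred percent as an efficiency.

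The protocol also refers to earlier descriptions that are not supplied. They may state the axes, so all that can be said is that the SAP sentence is not self-contained.

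**Conclusion.** The SAP sentence is loosely worded, and taken strictly it is wrong in one half. No change follows. The same paragraph shows which axes and which inversion are meant, and a literal misreading produces values (-20 to -50 W, or 400 to 500%, on the assumed ranges) that no analyst would report. The variables concerned are one secondary outcome and one that is arguably tertiary. The primary outcomes, the 0.05 significance level and the sample size statement do not depend on them.

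Writing out the axis and the reciprocal would record what a competent analyst would do anyway, and it would alter no treatment contrast. The mismatch itself is certain, being algebra. The judgement that it has no consequence rests on analysts recognising impossible values and on measurement error being alike under beetroot juice and placebo.
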